1.0 Study Summary

Study Title	Investigation of low-intensity focused ultrasound parameters
Study Design	Systematic study of set parameters in a multiple visit study
Primary Objective	Understanding the interaction of varying ultrasound parameters
Secondary Objective(s)	Document the tolerability of the parameters
Study Population	Healthy volunteers aged 18-65
Sample Size	80
Research Intervention(s)/ Investigational Agent(s)	Low-intensity focused ultrasound, Transcranial magnetic stimulation, EMG will be used to record motor responses.
Study Duration for Individual Participants	7 total study sessions, ~2.5 hours per session, for a total of ~17.5 hours.
Acronyms and Definitions	LIFU = low-intensity focused ultrasound TMS = transcranial magnetic stimulation MRI = magnetic resonance imaging CT = computed tomography EMG = electromyography ECG = electrocardiogram

2.0 Objectives

2.1 *Describe the purpose, specific aims, or objectives of this study:*

An understanding of the interaction of ultrasound parameters on human brain function is critical to rationally design clinically useful therapeutic methods that result in predictable outcomes. Experiments in small and large animal are confounded by small cranial vault size, anesthesia and thinner and differently shaped skulls making translation to human uncertain. Human studies remove translation and scaling issues and can be directly related for clinical use. Here, we will systematically test ranges of ultrasound parameters (intensity, duration, duty cycle, pulse repetition frequency) in a fully parametric design delivered to the primary motor cortex (M1) in healthy human volunteers. This will allow for an evaluation of what parameters change effect (and by how much), and determine how they interact with other parameters. Studies will be conducted in a cortical brain area using different outcome measures to test robustness and reproducibility.

2.2 *State the hypotheses to be tested:*

We hypothesize that duty cycles between 10 and 30% will result in inhibition and duty cycles > 50% will result in excitation independent of intensity and duration. We further hypothesize that longer durations will result in inhibition whereas shorter duration will

results in excitation. Finally, we hypothesize that 1000 Hz is the optimal PRF for these effects.

3.0 Background

3.1 *Summarize the relevant prior research on this topic and gaps in current knowledge within the field of study:*

Ultrasound has a rich parameter space. In addition to the fundamental frequency, parameters include intensity (directly relates to pressure), duration, number of cycles (relates to pulse duration), duty cycle and pulse repetition frequency (PRF). There are multiple studies in small and one in large animals explicitly testing how different parameters affect neuromodulation. King et al. (in mice) found that the product of intensity and duration best predicted success rates, Kim et al. (in rats) found a strong inter-dependency on duration and duty-cycle such that 300 milliseconds of LIFU at 50% duty cycle was most effective, and Yoo et al. (in rabbits) found PRF interacted with duty cycle such that high duty cycles (50%) at low PRFs (10 Hz) resulted in excitation whereas higher PRFs (100 Hz) at low duty cycle (5%) resulted in inhibition. In large animal (sheep), Yoon et al. reported inhibition was best achieved with a 3 and 5% duty cycle at PRFs of 60 and 100 Hz respectively and that 0.5 milliseconds at 70% duty cycle to be most effective for excitation. There are now several studies in primate and human showing neuromodulatory effect, though parameters have not been explicitly been tested.

Additionally, we have conducted a retrospective study of symptoms and safety in TMS and LIFU, which reported no serious adverse events in any of the studies monitored (Sci Rep 2020 [name]).

3.2 *Describe any relevant preliminary data:*

Primary motor cortex. We have collected $N = 6$ healthy participants under a full-parametric design looking at 3 intensities (6 W/cm², 12 W/cm², 24 W/cm² Isppa in the head), 6 duty cycles (1%, 5%, 10%, 30%, 50%, 70%), 3 durations (100 msec, 500 msec, 1000 msec) and 4 PRFs (10 Hz, 100 Hz, 500 Hz, 1000 Hz) delivered to the primary motor cortex using concurrent and concentric TMS/LIFU (Sci Rep 2018 [name]).

4.0 Study Endpoints

- 4.1 *Describe the primary and secondary **study** endpoints. See links below for discussion of study endpoints and how they may differ from study objectives. These are most common in clinical trials but are sometimes applicable to other types of biomedical research, as well as social, behavioral, or educational research. See link below for a discussion.*

https://docs.google.com/document/d/1Wocz7K7a0hCQJPPO_khh511SQQjhGDDGHzcOPRHR5Tw/edit?usp=sharing

Primary endpoint: Waveform combinations that induce reliable excitation and inhibition

Secondary endpoint: Documentation of tolerability of waveforms

- 4.2 *Describe any primary or secondary **safety** endpoints. These should be included for all studies that are greater than minimal risk. (Minimal risk: The probability and magnitude of harm or discomfort anticipated in the research that are not greater in and of themselves than those ordinarily encountered in daily life or during the performance of routine physical or psychological examinations or tests.):*

Primary safety endpoint: Subjective report questionnaire on neurological/physiological feelings.

Participants can request study procedures be stopped at any point throughout the experiment.

Based upon previous literature from our lab in humans we expect the LIFU effect to last up to 30 minutes. There is no evidence as yet that the proposed administration lasts longer than 30 minutes. All participants will be involved in laboratory procedures during this interval and be queried via the attached Report of Symptoms Questionnaire for any signs or symptoms from the LIFU intervention pre and post intervention.

Post-stimulation Monitoring:

Participants will be monitored for at least 30 minutes after stimulation has ended.

Participants will complete a Report of Symptoms questionnaire prior to leaving the facility. Responses will be monitored with each given session and the change of any symptom to 'severe' on the post-stimulation questionnaire compared to the pre-stimulation questionnaire will require PI evaluation.

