In addition to settings listed above, the following parameters are to be tested in this study. 3 Intensity (I) settings (6, 12, and 24 W/cm²), 6 duty cycle (DC) settings ranging from 1-70%, 3 duration (Dur) settings ranging from 100ms-1s, and 4 pulse repetition frequency (PRF) settings ranging from 10-1000Hz. As this is a parametric design, we are testing 216 ultrasound settings. Though each setting will take less than 1 minute to test, testing is

expected to be divided between 6 study sessions (up to 36 per session) to reduce burden to the participant.

These levels of energy are adhered to in human ultrasonic neuromodulation studies though there are no specific guidelines for energy deposition for ultrasonic neuromodulation and indeed, explicit expository and dosimetry for diagnostic and therapeutic applications, despite their prevalence and long history, has proven challenging and is still largely lacking. Ultrasound for transient neuromodulation is different from the use of ultrasound for surgery where very high intensities are used to thermally ablate tissues or for blood-brain barrier (BBB) opening where high intensities are also used in combination with contrast agents to intentionally produce cavitation as a means of opening the BBB. To date, a total of $N = 179$ in 8 published studies of healthy neurologically intact participants (plus one 1 TBI patient) have undergone a variant of LIFU for neuromodulation with no published report of severe adverse events. We have published on minor adverse events from LIFU ([name] et al. 2020).

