8.0 Procedures Involved

- 8.1 *Describe and explain the study design:*

This is a systematic study of set parameters in a multiple visit study.

Session 1: MRI and CT anatomical scans

Session 2-7: LIFU parameter testing with TMS and EMG while utilizing neuronavigation and physiological data collection such as PPG, BP, ECG, Respiration, and/or GSR.

- 8.2 *Provide a description of:*

- *All research procedures being performed*
- *If the study has more than one procedure, session, and/or subject population, describe each procedure, session, and/or study population separately. For complex studies, you are encouraged to include a figure or chart.*

Recruitment and Screening: Individuals indicating interest in participating in this research study will complete a screening and demographic form as part of the screening process (see Safety Screening Form and Demographic Form). This information will be reviewed to determine eligibility and to screen for any contraindications to MRI, CT, and TMS.

Consent: Participants will be asked to sign a consent form upon arrival for their first study visit. Participants will have as much time as they need to review the consent form and may ask questions of the PI or study team prior to participation.

Pregnancy Screening: Prior to any study procedures, female participants will provide a urine sample which will be screened for pregnancy. As indicated in the consent form, if

testing indicates the participant is pregnant, they will be notified and excluded from the study.

Participants will be healthy adults age 18-65 with no contraindications to MRI, CT, or TMS. We will enroll approximately 80 individuals.

This study includes low-intensity focused ultrasound (LIFU), transcranial magnetic stimulation (TMS), magnetic resonance imaging (MRI), and computed tomography (CT). Additionally, stereotaxic neuronavigation is utilized.

Study Procedures:

Session 1	Session 2-7
Imaging	36 Parameter Trials
MRI & CT	LIFU + TMS
2.5 hours	2.5 hours

*parameters per session will be chosen randomly within the set values

Session 1 - An MRI and CT exam will be performed and questionnaires will be administered.

Sessions 2-7 - Utilizing imaging collected on previous visit, subjects will complete a testing session. These sessions will involve LIFU and TMS stimulation. Additionally EMG, PPG, BP, ECG, Respiration, and GSR will be collected. Questionnaires will be administered at each session.

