Follow up - An electronic questionnaire of Report of Symptoms will be sent about 1 week following final study participation. If requested, this questionnaire can be completed verbally on the phone with study staff.

MRI session: Participants will receive an MRI scan to obtain a high-resolution image of their head to be used for proper setup of LIFU parameter sessions. During the MRI session, the experimenter and participant are able to communicate with one another at all times, ensuring the comfort of the subject. In addition, participants are provided with an emergency 'squeeze bulb' which can terminate the scanning procedure at any time.

CT session: Participants will receive a CT scan to obtain detailed imaging of the skull. CTs are collected as this is the only current option to properly image the skull. This is necessary for our computer models of acoustic wave propagation to ensure accurate intracranial intensities for each individual.

Stereotaxic neuronavigation: Stereotaxic neuronavigation allows us to track the positioning of the ultrasound transducer on the subject's head in real time using the MR/CT images for guidance.

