LIFU: Low-intensity focused ultrasound (LIFU) is a method of brain neuromodulation using ultrasonic acoustic energy. An ultrasound transducer is placed on the participant's head and is tracked using the neuronavigation system. Brief ultrasound pulses are delivered to the desired brain area. A small amount of ultrasound gel will be placed on the face of the single-element focused ultrasound transducer. The transducer will then be fitted on the scalp over the desired brain area and held in place with a mechanical arm. Brief pulses (0.1-1.0 seconds; duty cycle 1 – 70%; pulse repetition frequency 10 – 1000 Hz) of low-intensity (< 50 W/cm² Isppa), sub-thermal ultrasound (0.3 - 0.5 MHz) will be delivered in order to determine the area of activation, as well as the patterns of brain activity generated. Subjects may experience a mild buzzing sensation on their scalp depending upon stimulation parameters used. Participants will be familiarized with the sensations before formal testing. The ultrasound intensity used will be below the intensities recommended for the safe use of ultrasound by the FDA (190 W/cm² Isppa) and will be brief in duration at these low-intensities as not to generate any heating. While no discomfort is anticipated, participants will be informed if they experience any warming sensation on their scalp or discomfort to notify the investigator and the procedure will be immediately terminated. Participants may be given ear plugs to wear during the procedure and/or a white noise machine may be utilized in the testing space. This is to provide ear protection and noise cancellation to reduce participant focus on LIFU device function. We have significant experience using LIFU including our published reports of human neuromodulation experiments.

TMS: transcranial magnetic stimulation (TMS) is a noninvasive method of stimulating the brain using magnetically induced electrical currents. The stimulating coil is placed over a subject's motor cortex and a single pulse is conducted. This is repeated 10-20 times at an inter-stimulus interval of 5-10 seconds per trial. A threshold setting will be determined for each participant before each study session to obtain an average motor evoked potential of approximately 0.75mV, measured with EMG recordings. This will be the setting used throughout the testing session.

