Questionnaires: Questionnaires will be collected either electronically using a VT approved platform such as Redcap, or on paper. The following questionnaires will generally be completed during the imaging and consent visit but may be completed at following visits if time does not allow during the first visit: Beck Depression Inventory-II (BDI), Beck Anxiety Inventory (BAI), State Trait Anxiety Inventory (STAI), International Physical Activity Questionnaire (IPAQ), Medical Outcomes Survey Short Form-8 (SF-8), Sleep Scale from the Medical Outcomes Study, Patient Health Questionnaire-2 (PHQ-2), Generalized Anxiety Disorder 2-item (GAD-2), Tobacco, Alcohol, Prescription medications, and other Substance Tool (TAPS), and Perceived Stress Scale (PSS). Questionnaires may be used as a means of documenting potential confounds such as anxiety, fear, depression, etc. Questionnaires are estimated to take 30-45 minutes to complete. Additionally, the STAI (state only), Experience Questionnaire, Daily Questionnaire, and Report of Symptoms questionnaires will be administered at all stimulation sessions (sessions 2-7). The Daily Questionnaire exists to help quantify any variance between participant sessions. This includes items such as amount of sleep, hormone changes, and caffeine intake. Lastly, subjects will be contacted up to one month following the final session to complete the participant Report of Symptoms questionnaire. All questionnaires are attached to this application.

8.3 *Describe:*

- *Procedures or safeguards intended to reduce the probability and magnitude of risks. (For example: Reducing the risk of injury in a virtual reality study either by having the subjects sit during the study or by providing an obstacle-free space for walking.)*
- *Be sure to describe all drugs and devices used in the research, when they will be administered or used, and their purpose.*
- *Methods used to collect data about subjects. Please upload all data collection forms to Protocol Management. Some common examples are:*
 - *Screening questionnaires*
 - *Survey(s), including online surveys*
 - *Demographic questionnaire(s)*
 - *Interview guide(s), e.g., questions or pool of questions for semi-structured interviews*
 - *Focus group guide(s)*
 - *Other documents used to collect data*

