Participants will be screened for safety and any MRI, CT, TMS or ultrasound contraindications, including pregnancy testing. MRI and CT operators will utilize a microphone/headphone system to communicate after positioned in the scanner, while the scanner is not operating. A squeeze bulb is provided during MRI in order for the participant to indicate that they would like to stop or are uncomfortable. Study staff will be present throughout all LIFU/TMS procedures and they will be halted if the subject experiences any unexpected sensations. Breaks will be offered periodically to reduce participant discomfort. Monitoring for side effects will take place pre and post all stimulation sessions.

17.3 If applicable, indicate which procedures might have risks to the subjects that are currently unforeseeable. This will be rare, and usually applicable when testing a new drug or device or a new use of an existing drug or device:

N/A

17.4 If applicable, indicate which procedures might have risks to an embryo or fetus should the subject be or become pregnant:

CT should not be performed in pregnant women. Ionizing radiation can cause developmental problems in fetuses, particularly in the first trimester. Risks of using TMS with pregnancy women are currently unknown. Pregnant women will be excluded from this study. At the first study visit, study staff will screen for pregnancy in all females.

17.5 If applicable, describe risks to others who are not subjects (e.g., collection of sensitive health data that might affect sexual partners if disclosed, mandatory reporting of abuse, DNA testing that might affect family members or relationships):

N/A

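### The secondary endpoint is tolerability of waveforms, but symptoms are recorded per session of mixed settings and no tolerability analysis is planned, so the study as written documents tolerability of sessions

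*Protocol*

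**What the plan says.** **The endpoint.** Protocol 4.1 states "Secondary endpoint: Documentation of tolerability of waveforms". The secondary objective in protocol 1.0 is "Document the tolerability of the parameters".

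**The measurement.** Protocol 8.2 schedules the Report of Symptoms and the Experience Questionnaire at each of sessions 2 to 7. Protocol 17.2 says "Monitoring for side effects will take place pre and post all stimulation sessions", and 4.2 has responses reviewed session by session. One further report comes at the end: "An electronic questionnaire of Report of Symptoms will be sent about 1 week following final study participation" (protocol 8.2).

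**The content of a session.** Protocol 7.3 spreads 216 settings over six sessions, up to 36 in each. The table note in 8.2 adds that "parameters per session will be chosen randomly within the set values". Each trial carries 10 to 20 TMS pulses.

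**Events tied to one setting.** Participants who feel warming or discomfort are told "to notify the investigator and the procedure will be immediately terminated" (8.2, LIFU). Section 17.2 also halts stimulation for unexpected sensations.

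**The analysis.** Protocol 5.2 covers MEP and SEP amplitude only. The SAP's primary outcome is normalized MEP amplitude over 20 combinations, and its one secondary outcome is the effect of pulsing on MEP amplitude. It has no symptom, safety or tolerability outcome.

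**The concern.** The endpoint is defined for a waveform and the data are collected for a session. A headache reported after a session cannot be assigned to one of up to 36 settings. It cannot even be assigned to ultrasound, because the protocol lists headache for both LIFU (7.3) and TMS (17.1). A stop could identify one setting, but no passage asks for the active setting to be recorded at a stop, or for stops to count toward the endpoint.

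The study aims to find ultrasound parameters for later therapeutic use (protocol 3.3). As planned, a waveform could be reported as reliably excitatory or inhibitory with no tolerability figure beside it. The primary MEP endpoint is not affected.

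**Working it through.** **1. The plan's counts reproduce.** 3 x 6 x 3 x 4 = 216 settings; 216 / 6 = 36 per session; 80 x 0.70 = 56 completers. TMS pulses per session: 36 x 10 = 360 to 36 x 20 = 720.

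**2. What session reports could yield under the protocol design.** There are 56 x 6 = 336 session reports. Removing a level for each participant leaves 336 - 56 = 280 degrees of freedom for 215 contrasts among settings, and 280 - 215 = 65 residual. I simulated random splits of 216 settings into six sessions and took standard errors (SE) from the inverse of X'X after centring within participant. Assumptions not given in the documents: the sequence is logged, a session score is the sum of its setting effects, and residual SD is 1 both for a session score and for a single-setting rating.

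| Contrast | SE, session reports | SE, rating per setting |
|---|---|---|
| 70% vs 1% duty cycle, main-effects model | about 0.035 | sqrt(2 / (36 x 56)) = 0.031 |
| Two individual waveforms, all settings in the model | about 0.43 | sqrt(2 / 56) = 0.19 |

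Under the sum rule little is lost for a factor and much for a single waveform. If a participant's answer instead reflects the average of the 36 settings, the session SEs rise 36-fold: 36 x 0.035 = 1.26 for duty cycle and 36 x 0.43 = 15.5 for two waveforms. The documents do not say which rule is nearer the truth.

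**3. A simpler check.** Compare the 56 sessions that contain a given setting with the 280 that do not. Let b be the session symptom rate without it (assumed 10%, 20% or 30%), and let the setting cause a symptom in 10% of exposures. The rate with it is b + (1 - b) x 0.10, that is 19%, 28% or 37%. Power at two-sided 0.05 is 49%, 28% and 19%.

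**4. The SAP design.** 2 x 5 x 2 = 20 combinations, with no session split stated. Under the same model and assumptions as step 2:

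| Sessions used | SE, two waveforms |
|---|---|
| 1 | not estimable (rank 0) |
| 2 | 0.32 |
| 3 | 0.25 |
| 6 | 0.21 |
| rating per setting | 0.19 |

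One session is possible: 20 combinations x 20 stimulations x 5 s = 33 minutes, or 67 minutes at 10 s, within a 2.5-hour visit. Whether it will be done that way is not stated.

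**5. What setting-coded records would give.** No stops in 56 participants gives an exact two-sided 95% upper limit of 1 - 0.025^(1/56) = 6.4% for that waveform.

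**The case against.** The best defence is that the endpoint promises only documentation. Pre/post questionnaires, 30 minutes of observation and investigator review of any change to severe can describe tolerability without comparing waveforms. That is a fair reading of the word, and it is why a descriptive outcome is enough here. Even so, a description by waveform needs records by waveform.

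Second, the questionnaires and visit checklists are not in the documents, and a session form might ask about particular settings. It might, but both instruments are scheduled per session, and nothing in the text says they do.

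Third, stops are not the only signals that could be aligned with settings: respiration and other physiology are recorded, partly to look for ultrasound effects (8.2). This stands, but these signals are not symptom reports and neither document plans to analyse them for tolerability.

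Fourth, ratings after each setting have their own problems. Protocol 4.2 expects LIFU effects to last up to 30 minutes, while 7.3 allows under a minute per setting, so a rating may carry over from earlier settings. TMS soreness can build up during a session, and some stops will be due to TMS. These points stand and shape the fix; they do not supply the missing waveform data.

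A reader might infer that waveform tolerability cannot be estimated at all. For the protocol design that goes too far, because random mixing of settings permits indirect estimation. Nor does the point mean that participants go unmonitored: the stopping rules and the investigator's review are in place.

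**Conclusion.** The mismatch is real and should be fixed. The plan yields tolerability of sessions. Factor-level effects are recoverable only through an additive model that is not planned and a setting sequence that no passage requires to be logged. Individual waveforms are recoverable only indirectly and imprecisely, and not at all from session reports if the SAP's 20 combinations share one session.

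That the endpoint, the data capture and the analysis do not match follows from the text alone. The size of the loss does not. It is tempting to turn 0.43 against 0.19 into an effective sample, 56 x (0.19 / 0.43)^2, or about 11 participants instead of 56. The documents do not support that as a finding: it needs the sum rule, equal residual SDs and a model with a separate effect for every setting, which is not planned. Under the same sum rule, the duty-cycle contrast loses almost nothing. The SEs are best read as illustrating direction.

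**What to change.** 1. **Log events by setting.** At every stop, and at every unprompted report of warming, discomfort or unexpected sensation, record the active setting, its position in the session, and whether the sensation is attributed to LIFU, to TMS, or is unclear. Leave the stopping and withdrawal rules unchanged.
2. **One rating per setting.** After each setting's MEP block ends, record immediate discomfort (0 to 10) against the setting code. Ask the same question, in the same words, after the TMS-only baseline block.
3. **Add a descriptive secondary tolerability outcome to the SAP.** Report stops as n/N with exact two-sided 95% limits, where N is every enrolled participant who received the setting, not completers only. Report ratings by setting and by factor. Any model should have a participant effect and a term for position in the session. State that the results cover immediate sensation only and may include carryover from earlier settings.
4. **Keep the pre/post and follow-up questionnaires**, and report them per session as the record of delayed symptoms.

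**Cost.** 37 ratings (36 settings plus baseline) at 5 to 10 s take 3.1 to 6.2 minutes; for 20 combinations, 21 ratings take 1.8 to 3.5 minutes. A log field and a SAP paragraph are also needed, but no added participants, visits or stimulation. Time may be tight at the upper end: 36 x 20 x 10 s = 120 minutes, and the 30 minutes of observation then fill a 2.5-hour visit before set-up. Ratings also draw attention to the ultrasound, which 8.2 tries to limit with ear plugs or white noise. Asking only after the block, and identically at baseline, should reduce this but will not remove it.

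If the sponsor judges the rating too intrusive for the MEP measurement, step 1, step 3 for stops only, and step 4 still stand. The endpoint should then be restated as session-level tolerability plus stops by waveform.
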